### **6.2 Definition of serious adverse events**

An SAE is an event occurring from the time the patient signs informed consent (as per local regulations) through the end of the post-treatment follow-up visit (30 days post-last dose) or

until disease progression, whichever is the latest, which fulfils one or more of the following criteria:

- Results in death
- Is immediately life-threatening
- Requires in-patient hospitalization or prolongation of existing hospitalization
- Results in persistent or significant disability/incapacity or substantial disruption of the ability to conduct normal life functions
- Is a congenital abnormality or birth defect
- Is an important medical event that may jeopardize the patient or may require medical intervention to prevent one of the outcomes listed above.

For further guidance on the definition of an SAE, see [Appendix A](#) to the study protocol.

#### **Follow-up of unresolved adverse events**

Any AEs that are unresolved at the subject's last visit in the study are followed up by the investigator for as long as medically indicated, but without further recording in the CRF. AstraZeneca retains the right to request additional information for any subject with ongoing AE(s) at the end of the study, if judged necessary.

#### **6.2.1 Handling of deaths**

All deaths that occur during the study or within the follow-up period after the administration of the last dose of AZD9291 (30 days post-last dose) or until disease progression, whichever is the latest, must be reported as follows:

- Death, which is unequivocally due to disease progression, must be reported to the study representative and must be documented in the CRF, but must not be reported as an SAE during the study.
- Where death is not clearly due to progression of the disease being treated as part of the study, the primary and most likely event causing the death must be reported to AstraZeneca's representative as an SAE within 24 hours. The report must contain a comment regarding the co-involvement of progression of disease, if appropriate, and must assign a single primary cause of death together with any contributory causes.
- Deaths with an unknown cause must always be reported as an SAE but every effort should be made to establish a cause of death. A post-mortem may be helpful in the assessment of the cause of death, and if performed a copy of the post-mortem results must be reported in an expedited fashion to an AstraZeneca representative within the usual timeframes.

### 6.2.2 Hy's Law

Cases where a subject shows an AST or ALT  $\geq 3 \times \text{ULN}$  or total bilirubin  $\geq 2 \times \text{ULN}$  may need to be reported as SAEs. The investigator is responsible for, without delay, determining whether a subject meets potential Hy's law (PHL) criteria. Details of identification of PHL cases and actions to take are detailed in [Appendix C](#). Those SAE will be collected until 30 days post last dose of study medication.

## 6.3 Reporting of serious adverse events

All SAEs must be reported through the completion and submission of the SAE report form, from the time of signature of informed consent through 30 days post-last dose, whether or not considered causally related to AZD9291.

If any SAE occurs in the timeframe mentioned above, then the investigator or other site personnel must inform the appropriate AstraZeneca representatives within one day i.e., immediately but **no later than 24 hours** of when he or she becomes aware of it.

The designated AstraZeneca representative will work with the investigator to ensure that all the necessary information is provided to the AstraZeneca Patient Safety data entry site **within 1 calendar day** of initial receipt for fatal and life threatening events **and within 5 calendar days** of initial receipt for all other SAEs.

For fatal or life-threatening adverse events where important or relevant information is missing, active follow-up is undertaken immediately. Investigator or other site personnel must inform AstraZeneca representatives of any follow-up information on a previously reported SAE within one calendar day, i.e., immediately but **no later than 24 hours** of when he or she becomes aware of it.

The investigator or other study site personnel must report SAEs to the appropriate AstraZeneca representative through the completion and submission of the AstraZeneca SAE report form.

The AstraZeneca representative will advise the investigator/study site personnel how to proceed.

The reference document for definition of expectedness/listedness is the IB for the AstraZeneca drug AZD9291.

## 6.4 Overdose

There is no definition of what constitutes an overdose. In the Phase I study, 355 patients with advanced NSCLC were administered AZD9291 at single and multiple oral doses ranging from 20 mg to 240 mg daily (as of data cut-off date 02 December 2014). All doses were well tolerated. Experiences of excessive doses (i.e. in excess of the optimal 80 mg indicated dose) in this study did not show any DLTs or acute toxicities.

There is no known antidote. Investigators are advised that any patient, who receives a higher dose than intended should be monitored closely, managed with appropriate supportive care, and followed up expectantly.

Such overdose must be recorded in the CRF. If an overdose occurs in the course of the study, then the investigator or other site personnel inform appropriate AstraZeneca representatives immediately, or **no later than 24 hours** of when he or she becomes aware of it.

The designated AstraZeneca representative works with the investigator to ensure that all relevant information is provided to the AstraZeneca representative through the completion and submission of the overdose report form.

For overdoses associated with an SAE, the standard reporting timelines apply, see Section 6.3. For other overdoses, reporting must occur within 30 days.

## 6.5 Pregnancy

All pregnancies, including partner's pregnancy and outcomes of pregnancy, must be reported to AstraZeneca during the course of the study and within 30 days of the last dose of AZD9291 treatment through completion and submission of the pregnancy reporting form. (for partner pregnancies see Section 6.5.2)

### 6.5.1 Maternal exposure

If a patient becomes pregnant during the course of the study, AZD9291 treatment must be discontinued immediately.

Pregnancy itself is not regarded as an AE unless there is a suspicion that the AZD9291 may have interfered with the effectiveness of a contraceptive medication. Congenital abnormalities/birth defects and spontaneous miscarriages must be reported and handled as SAEs. The outcome of all pregnancies (spontaneous miscarriage, elective termination, ectopic pregnancy, normal birth, or congenital abnormality) must be followed up and documented even if the patient was discontinued from the study.

If any pregnancy occurs in the course of the study or within 30 days of the final dose of the AZD9291, the investigator or other site personnel must inform the appropriate AstraZeneca representatives within 1 day, i.e., immediately but **no later than 24 hours** of when he or she becomes aware of it. The designated AstraZeneca representative works with the investigator to ensure that all relevant information is provided to the AstraZeneca Patient Safety data entry site within 1 or 5 calendar days for SAEs (see Section 6.3) and within 30 days for all other pregnancies.

The same timelines apply when outcome information is available.

### 6.5.2 Paternal exposure

Pregnancy of the patient's partners is not considered to be an AE. However, the outcome of all pregnancies (spontaneous miscarriage, elective termination, ectopic pregnancy, normal

birth or congenital abnormality) should, if possible, be followed up and documented. If allowed by local regulations, information about a pregnancy from the partner of a male patient can be captured. If so, the male patient's partner consent must be obtained to collect information related to the pregnancy and outcome; the male patient should not be asked to provide this information. A consent form specific to this situation must be used. The outcome of any conception occurring from the date of the first dose until 6 months after dosing must be followed up and documented.

## 6.6 Management of toxicities related to AZD9291

If a patient experiences a CTCAE grade 3 or higher and/or unacceptable toxicity (any grade), where the investigator considers the event of concern to be specifically associated with AZD9291 (and not attributable to the disease or disease-related processes for which patient is being treated), dosing will be interrupted and supportive therapy administered as required in accordance with local practice/guidelines.

If the toxicity resolves or reverts to CTCAE grade  $\leq 2$  within 3 weeks of onset, treatment with AZD9291 may be restarted at the same dose (80 mg, daily) or a lower dose (40 mg, daily) using the rules below for dose modifications (Table 5) as per the investigator's evaluation and/or in discussion and agreement with the study Medical Monitor as needed. There will be no individual modifications to dosing schedule in response to toxicity, only potential dose reduction or dose interruption. Once a dose reduction is implemented, the dose of AZD9291 cannot be reverted back to 80 mg.

If the toxicity does not resolve to CTCAE grade  $\leq 2$  after 3 weeks, then the patient must be withdrawn from the study treatment and kept in observation until resolution of the toxicity.

**Table 5** Dose Interventions

Intervention	AZD9291 Dose
Starting Dose	80 mg daily
Reduced Dose	40 mg daily

If an event subsequently requires dose interruption, AZD9291 may restart at the same dose or the reduced dose, on resolution/improvement of the event at the discretion of the investigator.

### 6.6.1 Pulmonary Symptoms

If new or worsening pulmonary symptoms (e.g., dyspnea) or radiological abnormality suggestive of interstitial lung disease are observed, the administration of AZD9291 needs to be interrupted and the study Medical Monitor must be informed. It is strongly recommended to perform a full diagnostic workup, to exclude alternative causes such as lymphangitic carcinomatosis, infection, allergy, cardiogenic edema, or pulmonary hemorrhage. The results of the full diagnostic workup (including high-resolution computed tomography, blood and sputum culture, haematological parameters) will be recorded in the CRF by the investigator. Where ILD is suspected, local practice must be followed in discussion with the study Medical

Monitor. In the absence of a confirmed diagnosis of ILD, AZD9291 may be restarted following consultation with the study Medical Monitor. In case of a confirmed diagnosis of ILD, AZD9291 must be permanently discontinued. (refer to “Guidance for the Management of AE in studies using 80mg AZD9291”)

### **6.6.2 QTc Prolongation (using Fredericia’s formula –QTcF–)**

Patients with Grade 3 QTcF with QTcF prolongation (i.e., confirmed QTcF prolongation to > 500 ms absolute or a > 60 ms increase from baseline) should have AZD9291 interrupted and regular ECGs performed until resolution to baseline. If the QTcF interval resolves to Grade 1 (<481 msec), AZD9291 may be restarted at the reduced dose of 40 mg. If the QT prolongation does not resolve to  $\leq$ CTCAE grade 1 (<481 msec) after 3 weeks, then the patient will be permanently withdrawn from AZD9291 and observed until resolution of the toxicity.

All QTcF prolongation of >470 ms at any point during the study must be reported to AstraZeneca, and ECGs sent to the Study Team upon request for further analysis. This does not alter the management guidance outlined above.

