### 2.2 Violations and deviations

All major deviations related to the study inclusion or exclusion criteria and study conduct will be listed and summarised.

The following general categories will be considered major deviations. This list is not exhaustive and additional important deviations may be added prior to database lock.

- Informed consent procedure deviation Missing subject' signature from the informed consent document or other International Conference on Harmonisation - Good Clinical Practice (ICH-GCP) violation related to informed consent; laboratory or urinalysis samples or electrocardiogram (ECG) date before informed consent date and not performed per standard of care but on study purpose)
- Eligibility criteria deviation (any inclusion criteria not met or exclusion criteria met)
- Prohibited medication deviation (e.g., patients received other anticancer agents, investigational agents, or radiotherapy while on study treatment)
- Procedures/Tests deviation (ECG or ophthalmologic assessment or WHO performance status not performed at screening visit)
- Investigational product administration deviation (Overdose; Screening assessment date not within 28 days before start of treatment; Incorrect procedure for T790M obtainment; New or worsening pulmonary symptoms or radiological abnormality suggestive of Interstitial Lung Disease (ILD) observed, but study treatment not interrupted; Patient experiencing grade 3 QT interval corrected per Fredericia's formula (QTcF) with QTcF prolongation, but study treatment not interrupted)
- Withdrawal criteria deviation (Any withdrawal criteria met)
- Adverse Event (AE) / Serious Adverse Event (SAE) deviation (SAE / AE of special interest not reported in CRF within 24 hours of become aware)

The categorization of these as major deviations is not automatic and will depend on the duration and the perceived effect on efficacy.

All protocol deviations are defined in Protocol Deviation Specification document version 5.0 where a category Programmable / Observable is assigned to each deviation. Programmable deviations are programmed while Observable are checked manually during monitoring visits. Programmable deviations are then imported, and observable deviations are entered in a Protocol Deviation Tool according to classification defined in the Protocol Deviation

Specification. All deviations are then reviewed and classified on a monthly basis as Major/Minor.

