##### **Adverse Events of Special Interest (AESI)**

Summaries of the AESIs will include number (%) of patients who have:

- At least one AESI
- At least one AESI related to study medication. If causality is missing, assume that the AESI is related.
- At least one AESI leading to dose modification (reduction/interruption)
- At least one AESI leading to discontinuation

A summary of duration (days) of AESI will be provided for all events and this will be supported by summaries of events which have an end date, ongoing AESIs at death and, separately, at study discontinuation. All durations will be calculated.

Duration of Ongoing AESIs will be calculated using study discontinuation date as end date.

Duration of fatal AESIs will be calculated using death date collected on death form as end date.

Summary statistics of Time of Onset (days) from study treatment to start of AESI will also be provided for all AESIs.

Summary tables of AESIs providing the number (%) of patients experiencing any of the specified terms by maximum CTCAE grade will be also produced.

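### Protocol 6.6.2: the >60 ms QTcF trigger has no matching restart or withdrawal test, so below a 421 ms baseline one reading can meet both the interruption and the restart criteria

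*Protocol*

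**What the plan says.** **Trigger.** Protocol 6.6.2 opens with "Patients with Grade 3 QTcF with QTcF prolongation" and defines the condition as "confirmed QTcF prolongation to > 500 ms absolute or a > 60 ms increase from baseline". Either arm leads to interruption, and both carry the Grade 3 label.

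**Monitoring.** After interruption the protocol asks for "regular ECGs performed until resolution to baseline".

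**Restart.** "If the QTcF interval resolves to Grade 1 (<481 msec), AZD9291 may be restarted at the reduced dose of 40 mg".

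**Withdrawal within 6.6.2.** If QTcF has not come down to Grade 1 or lower, again given as below 481 ms, after 3 weeks, the patient leaves treatment permanently.

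**General rule.** Protocol 6.6 covers toxicity of grade 3 or higher that the investigator attributes to AZD9291. If it falls to grade 2 or lower within 3 weeks, "treatment with AZD9291 may be restarted at the same dose (80 mg, daily) or a lower dose (40 mg, daily". If it does not, the patient must come off study treatment. Once the dose has been reduced it cannot return to 80 mg.

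**Eligibility.** Exclusion criterion 6a in Protocol 3.2 removes patients with a mean resting QTcF above 470 ms. There is no lower limit.

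**SAP.** Section 2.2 lists, among the categories of major deviation, a patient with grade 3 QTcF "with QTcF prolongation, but study treatment not interrupted". Section 4.2.8 says that AESI tables "by maximum CTCAE grade will be also produced". QTc prolongation is one of the two AESIs (SAP 3.2.2).

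**The concern.** The trigger has an absolute arm and a change-from-baseline arm. The exit has only an absolute test. A patient interrupted because of the change from baseline therefore has no restart or withdrawal condition that refers to the reason for interruption. If the baseline is low enough, the reading is Grade 3 by the trigger and Grade 1 by the restart rule at the same moment.

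This is a cardiac safety rule. Two sites could read it differently for the same ECG: one resumes dosing because the value is below 481 ms, the other waits because the rise is still above 60 ms. A restart under 6.6.2 is at the reduced dose, and 6.6 makes that reduction permanent, so the choice lasts. If the rise persists, the instruction after 3 weeks depends on which grade label the site applies. The SAP refers to grade 3 QTcF in its deviation list and to CTCAE grade in its AESI table, so an unclear label could carry over into reporting.

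**Working it through.** The plan states no figure here to reproduce. The check is whether one reading can satisfy both rules.

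**Inputs.** Let B be baseline QTcF and Q a later confirmed reading, in ms.
- Interrupt (6.6.2): Q > 500, or Q − B > 60.
- Restart permitted (6.6.2): Q < 481.
- Withdraw (6.6.2): Q not below 481 after 3 weeks.
- Withdraw (6.6): drug-related toxicity not at grade 2 or lower after 3 weeks.
- Eligible baseline (3.2, criterion 6a): B ≤ 470, no lower limit.

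**Step 1: absolute arm.** Q > 500 and Q < 481 cannot both hold, so this arm is coherent with the restart test.

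**Step 2: change-from-baseline arm.** Q > B + 60 and Q < 481 can both hold when B + 60 < 481, that is, B < 421. In whole milliseconds the lowest triggering reading is B + 61 and the highest restart reading is 480. Overlap then needs B + 61 ≤ 480, so B ≤ 419.

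**Step 3: values in whole milliseconds.**

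| Baseline | First reading with rise >60 | Readings meeting both rules | Rise |
|---|---|---|---|
| 380 | 441 | 441–480 | 61–100 |
| 400 | 461 | 461–480 | 61–80 |
| 410 | 471 | 471–480 | 61–70 |
| 415 | 476 | 476–480 | 61–65 |
| 419 | 480 | 480 only | 61 |
| 420 | 481 | none | – |
| 440 | 501 | none | – |
| 470 | 531 | none | – |

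Listing every whole-millisecond baseline from 340 to 470 gives an overlap at each value from 340 to 419 and at none from 420 to 470.

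**Step 4: one patient followed through.** Take B = 400 and a confirmed Q = 465.
- Rise = 465 − 400 = 65 > 60, so 6.6.2 interrupts and labels the event Grade 3.
- 465 < 481, so the restart threshold, labelled Grade 1, is already met.
- Suppose Q is still 465 after 3 weeks. The 6.6.2 withdrawal test is not met, because 465 < 481. The interruption criterion is still met, because 65 > 60.
- Under 6.6, if the rise is attributed to the drug and keeps the Grade 3 label from the trigger, it has not reached grade 2 or lower and the patient must be withdrawn. If it takes the Grade 1 label from the restart sentence, 6.6 does not require withdrawal.

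The outcome at 3 weeks thus turns on which of two labels in one paragraph is applied to the same value.

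**The case against.** The strongest reply is that the paragraph describes a sequence. Prolongation is *confirmed*, treatment stops, ECGs follow, and drug *may* resume once the interval *resolves*. On this reading nobody is told to restart on the ECG that caused the interruption. That is fair: the text permits a restart and does not order one. But none of those words gives a criterion for resolution of a >60 ms rise, and the only number given is already satisfied.

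Several stronger claims that a reader might infer are not supported:
- **Restart and withdrawal contradict each other.** They do not. Both use the 481 ms cut. The conflict is between the trigger and that shared cut.
- **Withdrawal can never apply to such a patient.** The 6.6.2 test is unmet only while QTcF stays below 481 ms. Protocol 4.3 also allows discontinuation for QTc prolongation with signs or symptoms of serious arrhythmia, and for other unacceptable toxicity.
- **Monitoring to baseline is a second contradiction.** It sets how long ECGs continue. Its relation to restart is unclear, but that is an ambiguity.
- **6.6 and 6.6.2 conflict on restart grade and dose.** Section 6.6.2 reads naturally as a narrower, event-specific rule; 6.6.1 and 6.6.3 narrow 6.6 in the same way. Grade 1 and 40 mg lie within what 6.6 permits. Only the 3-week requirement in 6.6 can collide with 6.6.2, and only while the rise is still graded 3.
- **SAP tables will be wrong.** This is possible but not shown. A maximum-grade table is not lowered by a later Grade 1 reading, the CTCAE text is not in the documents, and SAP 2.2 says that classification as major is not automatic and points to a separate specification.

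On scale, Protocol Table 4 calls for on-treatment ECGs only on clinical indication or local standard of care, and all analyses are descriptive. The overall survival analysis does not depend on this rule.

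**Conclusion.** The point holds in this limited form. Protocol 6.6.2 treats a >60 ms rise as sufficient for interruption and labels it Grade 3, but tests restart and withdrawal only against an absolute value. For baselines below 421 ms, one reading can meet both the interruption and the restart criteria. While QTcF stays below 481 ms, a persisting rise never meets the 6.6.2 withdrawal test, whereas 6.6 would require withdrawal after 3 weeks if the rise is drug-related and still graded 3. The >500 ms arm is sound.

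The result rests on the stated thresholds alone, read literally, with *or* making either arm sufficient. It assumes nothing about how CTCAE grades such a rise. The number of patients affected cannot be stated, because the documents give no distribution of baseline QTcF and no expected frequency of rises above 60 ms. The case for correction is that a written safety rule conflicts with itself, not that a known number of patients is exposed.

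**What to change.** **Protocol.** The sponsor should reconcile the interruption trigger and its Grade 3 label with the restart, 3-week withdrawal and ECG-monitoring statements in 6.6.2, and with the 3-week rule in 6.6. The revised text should leave no reading that meets both the interruption and the restart criteria. The limits and the form of the rule are for the sponsor to decide; no view is taken here on which threshold, grade or dose is right.

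**SAP.** The deviation category in 2.2 for uninterrupted grade 3 QTcF, and the AESI summary by maximum CTCAE grade in 4.2.8, should then cite the same reconciled definition. Before any SAP wording relies on numeric QTcF, check that the CRF holds it: SAP 4.2.10 mentions only a yes/no flag for above 470 ms, an overall evaluation and clinical significance.

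**Cost.** A wording clarification in 6.6.2 and, if needed, 6.6, handled under the amendment process in Protocol 11.5, plus an aligned definition in the SAP and the deviation specification. Reconciling the wording does not in itself call for a new assessment or a change to any efficacy analysis.
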